##### **6.1.4.2 Evaluation of Non-Target Lesions**

Complete Response (CR): Disappearance of all non-target lesions and normalization of tumor marker level. All lymph nodes must be non-pathological in size (< 10 mm short axis).

Incomplete Response/Stable Disease (Non-CR/Non-PD): Persistence of one or more non-target lesion(s) and/or maintenance of tumor marker level above the normal limits.

Progressive Disease (PD): Appearance of one or more new lesions and/or unequivocal progression of existing non-target lesions

#### 6.1.4.3 Evaluation of Best Overall Response

The best overall response is the best response recorded from the start of the treatment until disease progression/recurrence (taking as reference for progressive disease the smallest measurements recorded since the treatment started). The subject's best response assignment will depend on the achievement of both measurement and confirmation criteria.

Time point response: patients with target (+/- non-target) disease.			
Target lesions	Non-target lesions	New lesions	Overall response
CR	CR	No	CR
CR	Non-CR/non-PD	No	PR
CR	Not evaluated	No	PR
PR	Non-PD or not all evaluated	No	PR
SD	Non-PD or not all evaluated	No	SD
Not all evaluated	Non-PD	No	NE
PD	Any	Yes or No	PD
Any	PD	Yes or No	PD
Any	Any	Yes	PD

CR = complete response, NE = not evaluable, PD = progressive disease, PR = partial response, SD = stable disease.

Time point response: patients with non-target disease only.		
Non-target lesions	New lesions	Overall response
CR	No	CR
Non-CR/non-PD	No	Non-CR/non-PD
Not all evaluated	No	NE
Unequivocal PD	Yes or No	PD
Any	Yes	PD

CR = complete response, NE = not evaluable, PD = progressive disease

A 'Non-CR/non-PD' is preferred over 'stable disease' for non-target disease since SD is increasingly used as endpoint for assessment of efficacy in some trials so to assign this category when no lesions can be measured is not advised.

#### 6.1.5 Duration of Response

Duration of overall response: The duration of overall response is measured from the time measurement criteria are met for CR or PR (whichever is first recorded) until the first date that recurrent or progressive disease is objectively documented

(taking as reference for progressive disease the smallest measurements recorded since the treatment started).

The duration of overall CR is measured from the time measurement criteria are first met for CR until the first date that recurrent disease is objectively documented.

Duration of stable disease: Stable disease is measured from the start of the treatment until the criteria for progression are met, taking as reference the smallest measurements recorded since the treatment started.

#### **6.1.6 Progression-Free Survival**

Progression-free survival (PFS) is defined as the duration of time from start of treatment to time of progression.

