### **2.2 Secondary Objectives**

- 2.2.1 To describe the adverse events associated with the administration of SABR to SRMs
- 2.2.2 To measure the growth rate of SRMs after SABR treatment.
- 2.2.3 To measure the changes in kidney function, creatinine levels, renal perfusion and GFR after SABR treatment.
- 2.2.4 To measure tumor viability pathologically one year after SABR treatment with a biopsy.
- 2.2.5 To assess radiographic changes of the SRM after SABR treatment, including tumor viability, %enhancement, necrosis, T2 signal, tumor cellularity with diffusion-weighted imaging
- 2.2.6 To assess local, regional and systemic progression of disease after SABR to SRM
- 2.2.7 To assess time to progression (TTP) of disease from the first SABR treatment.

- 2.2.8 To assess progression free survival (PFS). PFS is defined as the length of time from start of treatment to the time of loco-regional disease progression (as defined in Section 2.4) or death from any cause.
- 2.2.9 To assess overall survival (OS). OS is defined as the duration of time from start of treatment to the time of death from any cause.
- 2.2.10 To assess tumor growth, local failure and indeterminate disease response (IDR) as defined in section 6.1.4

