### **2.4.2 Secondary Endpoints:**

- 2.4.2.1 Adverse Events: Acute and late adverse events will be assessed using NCI's CTCAE v4.0 toxicity criteria and RTOG/EORTC criteria (Appendix A and B).
- 2.4.2.2 Growth Rate: Growth of the longest diameter of the SRMs after SABR treatment will be compared to baseline and expressed as growth rate of cm/year.
- 2.4.2.3 Loco-regional and systemic progression: Loco-regional and systemic progressive disease will be defined based on local, regional and systemic progression as defined by AJCC (7th edition) kidney cancer staging and any stage >T1a (>4cm) constitutes a progression.
- 2.4.2.4 Kidney function: To assess kidney function creatinine levels and renal perfusion scan will be performed at baseline and periodically after SABR (See section 5).
- 2.4.2.5 Radiographic changes: Radiographic changes of the SRM after SABR treatment will be assessed using MRI interpretation by a radiologist.
- 2.4.2.6 Tumor Growth, Local failure and Indeterminate Disease Response as defined in section 6.1.4

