## 9.3 Data Analyses Plans

The local control rate and the proportion of patients whose tumors did not grow will be estimated along with the corresponding 95% confidence interval using the exact binomial method. The frequency of the adverse events associated with the administration of SABR to SRMs will be computed. Descriptive statistics such as mean, range, and 95% confidence interval will be computed for the growth rate of SRMs after SABR treatment, and the changes in kidney function, creatinine levels, renal perfusion and GFR after SABR treatment. Descriptive statistics will be also computed for radiographic changes of the SRM after SABR treatment, including tumor viability, %enhancement, necrosis, T2 signal, and tumor cellularity with diffusion-weighted imaging.

Kaplan-Meier method will be used to estimate the time to progression (TTP) of disease from the first SABR treatment, progression free survival (PFS), and overall survival (OS). Exploratory data analysis will be conducted to assess the cytokine changes brought on by SABR to SRM and to evaluate generation of any immune response specific to tumor cells.

We will compute the following characteristics of CT and MRI acquired prior to the treatment and follow-up scan: intensity features such as minimum, maximum, mean, standard deviation, median, skewness, kurtosis; texture features such as energy, entropy, correlation, inertia, cluster shade; geometry features such as volume, major axis length, minor axis length, eccentricity, elongation, roundness. The ability of each feature to predict treatment response will be quantified by the area under the receiver operating characteristic curve (AUC). An AUC of <0.7 will be considered to have low accuracy, 0.7-0.9 to have moderate accuracy, and >0.9 to have high accuracy.

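### PFS is defined in two conflicting ways: Section 6.1.6 leaves out death, which turns PFS into TTP, and whether distant progression counts is ambiguous

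*Protocol*

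**What the plan says.** The protocol defines PFS twice.

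- Section 2.2.8 (secondary objectives) gives the "length of time from start of treatment to the time of loco-regional disease progression (as defined in Section 2.4) or death from any cause".
- Section 6.1.6 says "Progression-free survival (PFS) is defined as the duration of time from start of treatment to time of progression". It does not mention death, and it does not say which progression criterion is meant.

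Three other places bear on this.

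- Section 2.2.7 sets a separate objective: "To assess time to progression (TTP) of disease from the first SABR treatment".
- Section 9.3 plans Kaplan-Meier estimates of TTP, PFS and OS as three endpoints. It does not say which PFS definition applies.
- Section 2.4.2.3, the only progression definition in the section that 2.2.8 points to, reads "Loco-regional and systemic progressive disease will be defined based on local, regional and systemic progression as defined by AJCC" (7th edition). It adds that "any stage >T1a (>4cm) constitutes a progression".

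**The concern.** A patient who dies without progression has a PFS event under 2.2.8 and none under 6.1.6. In a Kaplan-Meier analysis a patient without an event is censored, so following 6.1.6 takes such deaths out of the endpoint. What remains is TTP under another name, although 9.3 lists the two separately.

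Follow-up runs for 2 to 5 years (Section 4.11; Section 5.3 schedules visits for five years). The possibility of death from other causes is acknowledged in Section 4.13. A PFS estimate that ignores those deaths would read too high. Two definitions in force also leave room to choose between them once the data are known.

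A second uncertainty concerns metastasis without local growth. The word loco-regional in 2.2.8 suggests that it is not an event. The cross-reference to Section 2.4 suggests that it may be.

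**Working it through.** **No figure to reproduce.** The precision and power statements in Section 9.2 concern local control, the proportion of tumours growing, and growth rate. None uses PFS.

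**Definitions side by side.**

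| Occurrence | 2.2.8 PFS | 6.1.6 PFS | 2.2.7 TTP |
|---|---|---|---|
| Loco-regional progression | event | event | event |
| Death without progression | event | not an event | not an event |
| Distant progression only | ambiguous | depends on a criterion not named | depends on a criterion not named |

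The 6.1.6 and TTP columns are identical. Both clocks start with SABR.

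**Illustration 1: deaths only.** Assume no progression and a constant annual other-cause mortality m; neither is given in the documents. Counting deaths, five-year PFS is (1 − m)^5. Under 6.1.6 there are no events, so the estimate is 100%.

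- m = 2%: 0.98^5 = 0.904, or 90%
- m = 5%: 0.95^5 = 0.774, or 77%
- m = 10%: 0.90^5 = 0.590, or 59%

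**Illustration 2: with some progression.** Assume constant, independent annual hazards: loco-regional progression l, distant-only progression d, and death without progression q. All are assumptions. At time T:

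- any progression or death: exp(−(l + d + q)T)
- 6.1.6, any progression counted and deaths censored: exp(−(l + d)T)
- 2.2.8 read narrowly, distant-only progression not counted and later hazards unchanged: exp(−(l + q)T)

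| T (years) | l, d, q | Any progression or death | 6.1.6 | 2.2.8, narrow |
|---|---|---|---|---|
| 2 | 0.02, 0.01, 0.02 | 0.905 | 0.942 | 0.923 |
| 2 | 0.02, 0.02, 0.05 | 0.835 | 0.923 | 0.869 |
| 2 | 0.02, 0.02, 0.08 | 0.787 | 0.923 | 0.819 |
| 5 | 0.02, 0.01, 0.02 | 0.779 | 0.861 | 0.819 |
| 5 | 0.02, 0.02, 0.05 | 0.638 | 0.819 | 0.705 |
| 5 | 0.02, 0.02, 0.08 | 0.549 | 0.819 | 0.607 |

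The 6.1.6 column does not respond to q: the second and third rows at each time agree although q differs. The last column applies only if 2.2.8 really excludes distant progression.

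**Does 2.2.8 exclude it?** The objective just before TTP, 2.2.6, names systemic progression outright: "To assess local, regional and systemic progression of disease after SABR to SRM". That favours reading loco-regional in 2.2.8 as a restriction. Against this, 2.4.2.3 treats loco-regional and systemic progression in one definition. The text does not settle the question.

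**Which progression?** Section 6.1.4.1 defines RECIST progression as growth of more than 20% and at least 5 mm over nadir. Section 2.4.2.3 uses a stage above T1a, that is, above 4 cm. If the treated mass is the only target lesion, the two rules meet at a nadir of 4 / 1.2 = 3.33 cm. Below that nadir, growth meets the RECIST rule first. Between 3.33 and 4 cm it crosses 4 cm first. The event date therefore depends on a choice that 6.1.6 does not make.

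**The case against.** The strongest reply is that 2.2.8 is sound as it stands. It counts death from any cause, and a loco-regional PFS is a reasonable endpoint for focal treatment of one renal mass, with systemic progression assessed separately under 2.2.6. This is right. A reader might infer that neither definition measures PFS; the documents do not support that for 2.2.8.

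It is also fair that distant progression is not plainly omitted. The cross-reference to Section 2.4 can bring it in. Under 6.1.6, if RECIST is the intended criterion, the tables in Section 6.1.4.3 make any new lesion progressive disease. The defect on this half is ambiguity.

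A reader might further infer that PFS would be overstated under either definition. That is not established. One PFS estimate is planned, and 2.2.8 does count deaths. The direction under 2.2.8 is also open, because Section 3.1.2 admits masses up to 5 cm while 2.4.2.3 calls anything above 4 cm progression, which could lower PFS. Nor does each metastatic patient necessarily move the estimate by 1/16 = 6.25 points: follow-up varies and patients may be replaced (Section 4.13), so Kaplan-Meier steps need not be 1/16.

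Finally, 6.1.6 does not mention censoring, detailed censoring rules may lie in a statistical analysis plan that is not shown, and the OS curve would still show the deaths. This softens the consequence. It does not remove the conflict, because the protocol itself fixes the event twice and differently.

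**Conclusion.** The conflict over death is real and explicit. Section 6.1.6, if followed, yields TTP labelled as PFS and an estimate that reads too high whenever patients die without progression. The illustrative gap at five years is 100% against 90% to 59%. It rests on assumed mortality of 2% to 10% a year and on no progression, and the 100% follows directly from that second assumption. Section 4.13 names death from other causes as a possible reason for losing a patient; it gives no rate.

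Whether distant progression counts is unclear, and so is the progression criterion behind 6.1.6. PFS is a descriptive secondary endpoint without a test. The primary endpoint, the sample size and the stopping rules do not depend on it.

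**What to change.** - Add death from any cause to the event in 6.1.6 so that it matches 2.2.8, and use one definition in both sections.
- State in both sections whether systemic progression under 2.4.2.3 is a PFS event. Counting it gives conventional PFS. If it is not counted, label the endpoint loco-regional PFS.
- Name the progression criterion that dates the event: 2.4.2.3 or RECIST progression in 6.1.4.
- Keep TTP as the progression-only endpoint.

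The cost is a short text change in two sections. Reported PFS may be lower. A reader might assume that every event needed is already collected, but the schedule in Sections 5.3 and 5.4 includes no distant-site imaging, so systemic progression would enter only as detected. The protocol should say so if it is counted. The primary endpoint and the sample size do not change.

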### **6.2 Pathologic Response:**

The pathologic response is evaluated by a required 1-year post-treatment biopsy where the tumor viability must be confirmed on FFPE tissue with appropriate staining (Ki67, PHH3, mitotic index etc.) showing continued tumor proliferation as compared to pre-treatment biopsy tissue.

### **6.3 Safety/tolerability**

Analyses will be performed for all subjects having received at least one fraction of radiation of study intervention. The study will use the CTCAE version 4.0 for reporting of non-hematologic adverse events (<http://ctep.cancer.gov/reporting/ctc.html>) and modified criteria for hematologic adverse events (Appendix #/letter).

## **7.0 ADVERSE EVENTS**

### **7.1 SABR**

The contraindications and adverse events for SABR are mostly related to the location of the SRM in relation to renal pelvis and its distance from loops of small bowel which is the most radio-sensitive organ nearby. The allowed radiation dose constraints of the kidney, small bowel and all the other nearby organs are discussed in detail in section 4.1

**7.1.1** Contraindications: None

**7.1.2** Special Warnings and Precautions for Use: N/A

**7.1.3** Interaction with other medications: None

### **7.2 Adverse Event Monitoring**

Adverse event data collection and reporting, which are required as part of every clinical trial, are done to ensure the safety of subjects enrolled in the studies as well as those who will enroll in future studies using similar agents. Adverse events are reported in a routine manner at scheduled times during a trial. Additionally, certain adverse events must be reported in an expedited manner to allow for optimal monitoring of subject safety and care.

All subjects experiencing an adverse event, regardless of its relationship to study intervention, will be monitored until:

- the adverse event resolves or the symptoms or signs that constitute the adverse

- event return to baseline;
- any abnormal laboratory values have returned to baseline;
- there is a satisfactory explanation other than the study intervention for the changes observed; or
- death.

### 7.2.1 **Definition**

An adverse event is defined as any untoward or unfavorable medical occurrence in a human research study participant, including any abnormal sign (for example, abnormal physical exam, imaging finding or clinically significant laboratory finding), symptom, clinical event, or disease, temporarily associated with the subject's participation in the research, whether or not it is considered related to the subject's participation in the research.

Adverse events encompass clinical, physical and psychological harms. Adverse events occur most commonly in the context of biomedical research, although on occasion, they can occur in the context of social and behavioral research. Adverse events may be expected or unexpected. **Acute Adverse Events**

An adverse event is defined as any untoward or unfavorable medical occurrence in a human research study participant, including any abnormal sign (for example, abnormal physical exam or laboratory finding), symptom, clinical event, or disease, temporarily associated with the subject's participation in the research, whether or not it is considered related to the subject's participation in the research. Adverse events occurring through the time period of [the start of treatment through the first follow up occurring 12 weeks post treatment](#) will be considered acute adverse events. All acute adverse events will be assessed and reported as per below.

### **Late Adverse Events**

Adverse effects occurring in the time period from the [end of acute monitoring](#), to 3 years post treatment for progression or death (whichever comes first), will be defined as late adverse events. These events will include all adverse events reported directly to a member of the study team and will be captured, assessed, graded and reported as appropriate.

In addition, the study team will review encounters in a select specialty category relevant to study endpoints. These select specialties include hospitalizations, medical oncology, and radiation oncology records and will be limited in scope based on categorization of events ([GU/GI](#)) and also the type of records that will be queried (hospitalizations, [medical oncology, and radiation oncology](#)).

An adverse event is defined as any untoward or unfavorable medical occurrence in a human research study participant, including any abnormal sign (for example, abnormal physical exam or laboratory finding), symptom, clinical event, or disease, temporarily associated with the subject's participation in the research, whether or not it is considered related to the subject's participation in the research.

Adverse events encompass clinical, physical and psychological harms. Adverse events occur most commonly in the context of biomedical research, although on occasion, they can occur in the context of social and behavioral research. Adverse events may be expected or unexpected.

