Radiation induced renal complications can be slow and non-inflammatory. The extent of radiation induced kidney damage is related to the volume of renal parenchyma receiving radiotherapy, total dose given to the kidney, dose per treatment, and other underlying medical conditions such as diabetes and hypertension. Acute radiation nephritis can be seen months after exposure to radiotherapy [48]. The clinical symptoms related to acute radiation nephritis include hypertension, edema, proteinuria, anemia, and uremia. In standard fractionated treatment to both kidneys about 50% of the patients will develop the clinical manifestation described above a dose of 23 Gy [49]. Among the clinical symptoms, the development of hypertension is the most important prognostic sign correlated with severe morbidity and death. However, when 50% or less of a single kidney is irradiated to a high dose (>26 Gy), clinical radiation induced nephropathy is rare [49].

In this phase II trial, the volume of high dose radiotherapy (>10 Gy) will be restricted to <50% of the entire kidney. The current study will also implement fractionated stereotactic radiosurgery to treat a unilateral kidney tumor. Fractionated radiotherapy is advocated to further reduce the potential toxicity arising from a large single fraction regimen. In fact, fractionated radiotherapy has been the standard treatment for many tumors in variety of locations to reduce the toxicity associated with radiotherapy. A fractionated stereotactic regimen has the potential to reduce the normal tissue toxicity that often accompanies radiotherapy.

Successful implementation of stereotactic radiosurgery of renal tumors may become an effective and the least invasive treatment modality. This study will refine the current understanding of the image guided conformal therapy to the kidney using stereotactic body radiotherapy.

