**4.11 Duration of Follow Up**

Subjects will be followed for 2-5 years with MRI scans every 6 months for the first year and if there is no growth then every six months subsequently; if there is evidence of growth, frequency will be determined by physician.

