**5.3 Follow-up Procedures**

Subject will be followed at every six months (+/- 2 weeks) thereafter for five years after their first follow up at 1 month (+/- 1 week).

With every visit, patients will have:

- Physical exam including: vital signs, weight, height and BMI
- MRI with or without contrast or CT with contrast
- Renal scintigraphy scan at 1 year
- Hematology
- Serum Chemistries
- Urine Analysis
- Lab corollary blood draw at 1 month and six month
- Performance status
- Toxicity evaluation
- Tumor measurements

**\*Note:** Subjects who show progressive disease or develop a new primary will be followed for survival only and will no longer strictly adhere to study calendar.

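### The late adverse event category closes at 3 years while toxicity visits run to 5 years, so toxicity found in years 4 and 5 belongs to no defined category

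*Protocol*

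**What the plan says.** Three sections of the protocol fix how long patients are observed for late toxicity, and they differ.

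- **Section 7.2.1, Late Adverse Events.** The late category starts when acute monitoring ends and runs "to 3 years post treatment for progression or death (whichever comes first"). On sources it says "These events will include all adverse events reported directly to a member of the study team". It then adds a review of records limited to GU/GI events: "These select specialties include hospitalizations, medical oncology, and radiation oncology records and will be limited in scope".
- **Section 5.3, Follow-up Procedures.** "Subject will be followed at every six months (+/- 2 weeks) thereafter for five years after their first follow up" at one month. The procedures listed for every visit include "Toxicity evaluation", vital signs, chemistry and urine analysis. The Time and Events Table (5.4) repeats the six-monthly toxicity evaluation. A note in 5.3 moves patients with progressive disease or a new primary to follow-up for survival only.
- **Section 4.11, Duration of Follow Up.** "Subjects will be followed for 2-5 years with MRI scans every 6 months for the first year", and six-monthly after that if there is no growth.

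The results that depend on these windows are secondary objective 2.2.1 (describing the adverse events of SABR), endpoint 2.4.2.1 (acute and late adverse events, graded by CTCAE v4.0 and RTOG/EORTC), and the adverse event frequencies in section 9.3.

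**The concern.** The endpoint names two categories, acute and late. The acute category ends about 12 weeks after treatment and the late category ends at 3 years. A toxicity first found at a year-4 visit is therefore neither, although the protocol schedules the visit at which it would be found. The guidelines in Appendix B add to the mismatch: after day 90 the late-effects scale is to be used, with no end date, so the year-4 event would be graded on the late scale without being a late adverse event.

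Section 1.3 says that radiation damage to the kidney can develop slowly, and reports one late grade 3 renal dysfunction in the 15-patient phase I study. With 16 patients here, including or omitting a single event visibly changes a reported frequency (1/16 = 6.25%). Two analysts applying the same protocol could report different late-toxicity counts.

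**Working it through.** The protocol states no figure for this point, so there is none to reproduce. The check compares the windows and counts visits.

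**Inputs**

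| Item | Value | Source |
|---|---|---|
| End of late window | 3 years (36 months) post treatment | 7.2.1 |
| Length of visit schedule | 5 years, every 6 months | 5.3, 5.4 |
| Toxicity evaluation at each visit | yes | 5.3, 5.4 |
| Stated follow-up range | 2 to 5 years | 4.11 |
| Sample size | 16 | 9.2 |

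**Visits after month 36**

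1. Intervals counted from treatment: month = 6k, k = 1 to 10, giving 6, 12, 18, 24, 30, 36, 42, 48, 54, 60. Those after month 36 are 42, 48, 54 and 60, so 4 of 10.
2. Intervals counted from the 1-month visit, which section 5.3 also permits: month = 1 + 6k, giving 7, 13, 19, 25, 31, 37, 43, 49, 55, 61. Those after month 36 are 37, 43, 49, 55 and 61, so 5 of 10.
3. In calendar time, (5 − 3)/5 = 40% of the five-year schedule lies beyond the window.
4. The ±2-week tolerance means that, under count 1, a month-36 visit can fall on either side of the limit.

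**Dependence on actual follow-up (count 1)**

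- Followed 2 years (the minimum in 4.11): 0 of 4 visits outside.
- Followed 3 years: 0 of 6.
- Followed 4 years: 2 of 8 (months 42 and 48).
- Followed 5 years: 4 of 10.

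Across the trial, the ceiling under count 1 is 16 × 4 = 64 of 16 × 10 = 160 visits. It is reached only if every patient completes five years without moving to survival-only follow-up.

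**The progression/death clause**

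The likely meaning is that the window closes at the earliest of 3 years, progression or death. The word linking the 3 years to progression does not say this, and the clause could also be read as describing what the treatment or the follow-up is for. The first reading agrees with the note in 5.3, because patients who progress no longer follow the study calendar. The clause should say so plainly.

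**The case against.** The strongest reply is that the 3-year limit governs a label and is not shown to govern the data or the analysis. Much of this stands:

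- The general definition of an adverse event in 7.2.1 has no end date.
- Section 4.9 assesses every treated patient by the Time and Events Table, with no 3-year limit.
- Section 7.3 requires reporting of treatment-attributed events later than 30 days after the last dose, with no end date.
- Section 9.3 computes frequencies of adverse events associated with SABR without restricting them to the late category.
- Renal function (creatinine, perfusion, GFR) is a separate secondary objective, analyzed without reference to the adverse event window.

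A year-4 event is therefore mislabelled or at risk of omission. It is not shown to be dropped. The mismatch itself remains, because endpoint 2.4.2.1 is worded in terms of acute and late events.

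A reader might go further in four ways that the documents do not support.

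1. **Hypertension goes uncaptured because record review is limited to GU/GI.** That review is only an addition to the capture of all directly reported events, whatever the organ system. Vital signs are taken at every visit, and section 5.1.6 includes blood pressure among them. The KIDNEY row of Appendix C grades hypertension, so it is not clearly outside GU. The statement in 1.3 that "the development of hypertension is the most important prognostic sign correlated with severe morbidity and death" concerns acute radiation nephritis within months of exposure and has no bearing on years 4 and 5. What remains is narrow: the review does not name hypertension, and hypertension managed outside the listed record types between visits could be missed by it.
2. **A large share of late events is lost.** Under an assumed constant hazard of 3% per year, incidence is 1 − exp(−0.09) = 8.6% at 3 years and 1 − exp(−0.15) = 13.9% at 5 years, so (13.9 − 8.6)/13.9 = 38% would arise after year 3. The share is 39% at 1% per year and 34% at 10%. No passage supports any of these rates or a constant hazard. A front-loaded hazard would give less and a rising one more.
3. **SABR will look safer than observed.** This needs analysts to exclude the events, which section 9.3 does not instruct.
4. **Events after progression should also be counted.** Section 5.3 moves these patients to survival-only follow-up, and section 1.3 offers them surgery or ablation, which would confuse attribution. Closing the window at progression is a defensible choice.

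**Conclusion.** The contradiction is real and should be corrected. The late adverse event category ends at 3 years, toxicity evaluation is scheduled to 5 years, and section 4.11 states a third duration. For a patient who completes five years, 4 of 10 six-monthly toxicity visits (5 of 10 counting from the 1-month visit) fall in no adverse event category. For a patient followed three years or less, the gap does not arise under the first count.

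The consequence is ambiguity in endpoint 2.4.2.1 and objective 2.2.1, with a possibility of under-counting if the definition is applied literally. This rests on the wording of 7.2.1 and 2.4.2.1 and on patients actually being followed beyond year 3. It needs no assumption about event rates, and no number of missed events can be derived from the protocol. The statistical analysis plan, not available here, might state which events are tabulated, but the protocol's own durations would still disagree.

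**What to change.** 1. Reconcile the durations in 4.11, 5.3 and 7.2.1, and state whether six-monthly visits are counted from treatment or from the 1-month visit.
2. In 7.2.1, define late adverse events as those occurring from the end of the acute window to the patient's last protocol toxicity visit, up to 5 years.
3. Reword the progression/death clause so that its effect on the window is explicit and agrees with survival-only follow-up after progression in 5.3.
4. Optionally, state that the supplementary GU/GI record review includes hypertension and renal-function events.

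The visits, vital signs and laboratory tests are already scheduled, so no new assessments are needed. The cost is an amendment to the definitions and modest extra event abstraction in years 4 and 5.
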